### **9.2 SAMPLE SIZE DETERMINATION**

Data will be tested for normality using the Shapiro-Wilk test. Continuous variables will be described as mean  $\pm$  standard deviation (SD) if normally distributed. Variables with skewed distribution (i.e. aldosterone, BNP, etc.) were logarithmically transformed prior to analyses and are presented as median and interquartile range (IQR). Categorical variables will be expressed as numbers (percentages).

When data are normally distributed, comparisons between the treatment (sodium intake) and control (placebo) groups will be made using paired Student's t-tests, and when data are non-

[figure not shown]
normally distributed, the Mann-Whitney U test will be employed. Chi-square test will be used for categorical variables. Tests for sodium intake effect on the primary outcomes without correction for period effect will be done using Mann-Whitney test on the differences. Tests for period effect will be assessed using two-sample Wilcoxon tests on the differences between treatment groups, and tests for carry-over effect will be assessed by a two-sample Mann-Whitney test on the averages in the two treatment periods. Correlations were determined with Pearson's correlation coefficient.

Additionally, we will evaluate the effects of sodium intake on changes in blood pressure, 24-hr ambulatory blood pressure monitoring (ABPM), biochemical markers, vascular functions, and specific transcriptome and epigenome by using a linear mixed model, with subject as a random effect, thereby accounting for the period, sequence, and carryover effects and to model the various sources of intra-individual and inter-individual variability. All statistical tests will be two-sided and P values  $<0.05$  will be regarded as significant. Statistical analyses will be carried out using SAS software (SAS Institute, Inc., Cary, NC, USA).

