The output of the pipelines are count data which are discrete, not continuous, and include only positive values. The counts,  $C_{ij}$ , are the observed number of microbes for the  $i^{th}$  sample and  $j^{th}$  feature where the features are the OTUs or microbial taxa. The data are normalized because library sizes (total counts for each sample, across all features) often have a large magnitude difference, which can cause a bias. The data are right skewed with, usually, a large number of data points having the value 0. Such data follows a Poisson distribution and therefore a Poisson regression model type (e.g. negative binomial model) will be used to investigate the relationship between microbiome and salt intake. For each feature, a model will be fitted with the feature as outcome and salt intake (a binary variable with two categories: treatment and placebo) as covariate. The differential count (fold change difference) between treatment and placebo will be estimated for each feature (OTU). To adjust for the multiple testing of several OTUs, a false discovery rate penalty will be applied and only fold changes with an adjusted p-value (Benjamini-Hochberg multiple test correction) smaller or equal to 0.05 will be considered statistically significant.

The analysis describes above using a Poisson regression model assumes the features (OTUs) are independent but it has been shown that microbial communities do interact in such way that changes in one feature affect another feature. However, the number of interactions can be large due to the number of features, and not easily fitted in a conventional regression model. Therefore, a machine learning algorithm (Random Forest or Neural Network) will be used to investigate the combined response of the features to salt intake. These algorithms can incorporate multiple and complex interactions between features without making an assumption about their distribution. The features will be used as predictor variables to predict salt intake (a binary variable with two categories: treatment and placebo). The results will be presented as the area under the curve (AUC) of a receiver operating curve (ROC) that reflect how well the features can predict treatment and placebo. Because these ensemble techniques do not assume the predictors

variable (OTUs) are independent, no multiple testing penalty is required but rather cross-validation will be undertaken.

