#### 9.4.3 Analysis of the Secondary Endpoint(s)

The secondary endpoints will be assessed independent of the results associated with the primary endpoints; secondary endpoints include blood pressure, whole blood epigenome, and whole blood and urine transcriptome. The effect of treatment and placebo will be investigated will be investigated for each secondary endpoint, as detailed below.

The association between blood pressure (systolic and diastolic) and salt intake will be assessed using multiple linear regression with salt intake (two categories: treatment and placebo) as the exposure variable and blood pressure outcome variable. The effect size, p-value and 95% confidence interval of the regression model will be provided as results.

The effect of salt intake on gene expression will be investigated in a differential expression analysis to identify genes whose expression differs significantly between treatment and placebo. The gene expression data will be normalized, using the weighted trimmed mean of M-values (TMM) method, an optimal method for the normalization of mRNA count data. Genes with an expression less than 1 Count Per Million (CPM = count/sum [counts] x 1million) in at least 2 samples will be excluded because results from genes with extremely low expression are not reliable. Gene expression is generated as count data which follows a Poisson distribution; therefore, a negative binomial model will be fitted using the R library *edgeR* developed to handle the specificities of mRNA sequencing data. The model computes likelihood ratio tests for the coefficients whilst taking into account dispersion. A deviance of goodness of fit test will be carried out to identify genes where the model fit was poor indicating that the dispersion estimate is away from the average dispersion. Dispersion outliers will not be considered for the results because the deviance indicates low quality or marked expression difference for the gene. Finally, genes with a log fold change not equal to 0 and a false discovery rate adjusted p-value  $\leq 0.05$  will be reported as significantly differentially expressed between treatment and placebo. Multiple testing correction, for the total number of genes considered, will be carried out using the Benjamini-Hochberg method.

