The epigenetic effect of salt intake will be investigated through a two-sample t-test to identify methylation sites with significant methylation level difference between treatment and placebo. At a minimum of 5X coverage and an average coverage of 30X, the SureSelect-MethSeq (SS-Methseq) platform captures between 2.6 and 2.3 million methylation sites. After thorough processing and QC of the methylation data, using the Bismark pipeline, samples and methylation sites that passed all QC filters will be considered for the analysis. Each methylation site will be treated as a continuous variable and salt intake will be treated as a nominal variable with two categories (treatment and placebo), in the t-test. In such analysis, the methylation sites are assumed to be independent and there is, hence, a high burden of multiple testing due to the millions of sites being tested. Therefore, a significance threshold of p-value  $< 9 \times 10^{-8}$  will be applied to control for false positive findings; this threshold was derived from empirical work based on the Illumina EPIC array which has a lower density than the SS-Methseq platform but includes carefully selected sites that span the whole genome. The estimated mean difference, p-value and 95% confidence interval of the t-test will be presented as the results.

After the transcriptome, epigenome and microbiome data have been considered separately in the analyses described above and to understand the links between gene expression and methylation, an ensemble technique such as Random Forests will be used to leverage the high dimensionality of the data (number of features >> number of observations) and identify the best combination of predictors of salt intake in the transcriptome and epigenome data. Subsequently, the OTUs identified in the microbiome data will be integrated to find out if microbiome information improves the prediction accuracy of the omics data. This will provide further insights into the interplay between the three domains (microbiome, transcriptome and epigenome).

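### The only significance rule section 9.2 states for its mixed model on selected transcriptome and epigenome features is P<0.05 with no multiplicity adjustment, so a gene or site that fails section 9.4.3 can still be declared significant

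*Combined protocol and SAP*

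**What the plan says.** Section 9.2 lists the outcomes for a linear mixed model: blood pressure, ambulatory blood pressure, biochemical markers, vascular function and "specific transcriptome and epigenome by using a linear mixed model, with subject as a random effect". The features are not named or counted, and are not tied to the results of another analysis. The next sentence, "All statistical tests will be two-sided and P values", goes on to make values below 0.05 significant. It has no exception for omics data and no pointer to section 9.4.

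Section 9.4.3 covers the same two domains differently.

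- **Transcriptome.** A negative binomial model is fitted in edgeR. The features reported are "genes with a log fold change not equal to 0 and a false discovery rate adjusted p-value" of at most 0.05, and "Multiple testing correction, for the total number of genes considered, will be carried out using the Benjamini-Hochberg method".
- **Epigenome.** "The epigenetic effect of salt intake will be investigated through a two-sample t-test to identify methylation sites". The cut-off, introduced by "Therefore, a significance threshold of p-value", is 9e-8, and the plan says that it "will be applied to control for false positive findings".

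The opening of section 9 says there will be no formal statistical analysis plan, and section 9.4.9 rules out exploratory analyses.

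**The concern.** The thresholds in 9.4.3 are each attached to a particular model: edgeR for genes and a per-site two-sample t-test for methylation. The mixed model is a third analysis and appears only in 9.2, so the only significance rule written for it is 0.05. Someone following the plan literally could test a handful of genes or sites in the mixed model and report those below 0.05 as significant, although the same features had failed the rule in 9.4.3.

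Whole blood epigenome and whole blood and urine transcriptome are declared secondary endpoints. Whether salt is said to change them could depend on which section is cited. Because the features are not fixed in advance, they could also be chosen after the genome-wide results are known. No other planned document would settle the matter, and the plan leaves no exploratory category in which to place these results.

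**Working it through.** **1. The plan's own figure.** The inputs, all from section 9.2, are a PWV difference of 0.6 m/s, SD 0.9 m/s per condition, within-subject correlation 0.3, 80% power, significance level 0.05 and a paired t-test.

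- SD of the paired difference = 0.9 × √(2 × (1 − 0.3)) = 1.065 m/s.
- Normal approximation: n = (1.065 × (1.960 + 0.842) / 0.6)² = 24.7, so 25.
- Noncentral t: n = 27 gives power 0.805 and n = 28 gives 0.820.

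The stated 28 is reproduced to within one participant. PWV was thus sized at two-sided 0.05 as a single outcome. This says nothing about using 0.05 for omics features.

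**2. The rules side by side.**

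| Domain | Section 9.2 | Section 9.4.3 |
|---|---|---|
| Genes | Mixed model on selected features; P<0.05, no adjustment stated | edgeR negative binomial; Benjamini-Hochberg adjusted P ≤ 0.05 over all genes considered |
| Methylation sites | Mixed model on selected features; P<0.05, no adjustment stated | Two-sample t-test per site; P<9e-8 |

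**3. How far apart the rules are.**

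- Methylation: 0.05 / 9e-8 ≈ 556,000. As an illustration on a common scale, with 27 degrees of freedom (28 paired participants) the critical |t| is 2.05 at 0.05 and 7.23 at 9e-8. With 39 degrees of freedom (40 participants) it is 2.02 and 6.55. A site with P = 0.001 meets the first rule and fails the second.
- Genes: Benjamini-Hochberg calls a gene when its raw P is at most 0.05 × R/m, where R is the number of genes called and m the number tested. A gene with raw P = 0.01 is called only if R/m ≥ 0.01/0.05 = 0.2, that is, if at least one fifth of all genes tested are called. Otherwise it fails 9.4.3 while meeting 0.05.

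The mixed model can also give a different P from edgeR or the two-sample t-test for the same feature, so the two routes differ in both the P value and the bar.

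**4. False positives through the mixed-model route.** The documents give no feature count, so k is assumed. For k independent null features chosen without looking at the data, P(at least one false hit) = 1 − 0.95^k.

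| k (assumed) | Calculation | Chance of at least one false hit |
|---|---|---|
| 5 | 1 − 0.774 | 23% |
| 10 | 1 − 0.599 | 40% |
| 20 | 1 − 0.358 | 64% |

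If features are picked because they ranked high in the screen on the same participants, the chance is higher, since the mixed model then largely re-tests differences already selected for being large. If the features were restricted to those that had passed 9.4.3, little harm would follow, but 9.2 does not say so.

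**The case against.** The strongest reply is that the specific rule overrides the general one. Section 9.2 never says the P value is unadjusted, and a Benjamini-Hochberg adjusted P compared with 0.05 is consistent with its sentence. Section 9.4.3 justifies the methylation cut-off by the burden of testing millions of sites. The paragraph in 9.2 names SAS while the gene analysis uses edgeR in R, which suggests 9.2 was drafted mainly with conventional outcomes in mind.

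Much of this stands. It settles the genome-wide screens and the microbiome count analysis. It does not settle the mixed model, which explicitly includes transcriptome and epigenome features and has no rule of its own in 9.4.

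Three stronger readings are tempting, and the documents do not support them.

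- **Mass false discovery.** A reader might multiply the 2.3 to 2.6 million sites by 0.05 and expect 115,000 to 130,000 false sites. That needs raw 0.05 on every site. The only genome-wide methylation test in the plan carries 9e-8, and 9.2 limits the mixed model to specific features.
- **The microbiome is caught too.** It is not among the mixed-model outcomes. Section 9.2 does apply rank tests to the primary outcomes, but does not say these are run per taxon. For taxon-level fold changes section 9.4.2 is explicit: "only fold changes with an adjusted p-value (Benjamini-Hochberg multiple test correction) smaller or equal to 0.05 will be considered statistically significant".
- **The mixed model is the only within-person analysis, so its results will be the ones quoted.** Section 9.2 also names paired t-tests and bases the sample size on one.

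**Conclusion.** Wrong as written, within a narrow scope. Followed literally, section 9.2 lets a gene or methylation site that fails 9.4.3 be declared significant through the mixed model. The text itself shows the conflict and no arithmetic is needed to establish it.

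The size is conditional: 23%, 40% and 64% rest on assumed counts of 5, 10 and 20, on independence, on every feature being null, and on selection made without sight of the data. Correlation among features would change the figures, and selection from the screen would raise them. Two secondary endpoints are affected. Nothing here questions two-sided 0.05 as the level used to size the PWV comparison.

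**What to change.** Amend section 9.2, before the omics results are analysed, to say the following.

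- Raw two-sided P<0.05 applies to single-outcome tests: PWV, blood pressure and biochemical markers.
- Significance claims for transcriptome and epigenome features rest on the analyses and thresholds in 9.4.3.
- Mixed-model results for features picked from the screen are reported as estimates with confidence intervals and carry no new significance claim.
- Features to be tested in the mixed model in their own right are named before the data are seen, and tested with a multiplicity correction, for example Benjamini-Hochberg, over the number tested.

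The last item avoids holding a short list named in advance to 9e-8, which was set for a genome-wide search. Making 9.4.3 the basis for the screen also deals with the two models giving different P values for one feature.

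The cost is a few sentences, with no new data, participants or procedures. The downside is that fewer omics features can be called significant.

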**Figure 2.**

### 9.3 POPULATIONS FOR ANALYSES

We will use the per-protocol analysis dataset for our study. We are confident that participants will comply with the protocol sufficiently to ensure that the data will be likely to represent the effects of exposure to treatment and placebo arms based on the underlying scientific model.

#### 9.3.1 Evaluable for toxicity

#### 9.3.2 Evaluable for objective response

Not applicable

#### 9.3.3 Evaluable Non-Target Disease Response

Not applicable

### 9.4 STATISTICAL ANALYSES

#### 9.4.1 General Approach

For descriptive statistics, categorical variables will be assessed via chi-square and presented as percentages. Continuous variables will be assessed via t-test and will be presented as means with standard deviations. We will check assumptions underlying statistical procedure and correct procedure if necessary.

#### 9.4.2 Analysis of the Primary Endpoints

The two primary endpoints are vascular function and microbiome.

First, vascular function difference between placebo and treatment (salt intake) will be estimated. Then, microbiome differential between treatment and placebo will be identified and estimate for each of the microbiome collection sides (skin, oral and gut). Details of the vascular function and microbiome analyses with respect to treatment and placebo are provided below.

Vascular function (e.g. pulse wave velocity, PWV) will be first analyzed as a continuous variable. Its relationship with salt intake will be investigated through multiple linear regression with vascular function as outcome and salt intake (a binary variable with two categories:

treatment and placebo) as exposure variable. For this analysis only samples with complete data for vascular function and salt intake will be considered. The outcome variable will be log transformed if it departs markedly from the Gaussian distribution. The aim of this first analysis is to estimate the effect of salt intake on vascular function. The effect size, p-value and 95% confidence interval will be provided as results.

The second endpoint is microbiome; the microbiome data of each of the all the collection sites (oral, gut and skins) will be analyzed separately. Prior to investigating the relationship between microbiome and salt intake, the raw microbiome data requires extensive processing and quality controls (QC) because of challenges posed by this type of data and the potential of spurious results if appropriate QC are not applied. The raw data will be processed in mainly 5 steps: (a) reads preparation (assembly of paired reads, filtering of low quality reads and identification of unique sequences), (b) Operational Taxonomic Units - OTU clustering (selection of unique OTU sequences), (c) quality controls (identification and removal of artifacts from amplicon reads, in OUT sequences). These tasks will be carried out using pipelines included in the standards operating protocols (SOPs) developed and used by the NIH Human Microbiome Project. For the metagenomic microbiome data, the *HUMANN2* pipeline will be used and for the 16s microbiome data the *DADA2* pipeline will be used.

The output of the pipelines are count data which are discrete, not continuous, and include only positive values. The counts,  $C_{ij}$ , are the observed number of microbes for the  $i^{th}$  sample and  $j^{th}$  feature where the features are the OTUs or microbial taxa. The data are normalized because library sizes (total counts for each sample, across all features) often have a large magnitude difference, which can cause a bias. The data are right skewed with, usually, a large number of data points having the value 0. Such data follows a Poisson distribution and therefore a Poisson regression model type (e.g. negative binomial model) will be used to investigate the relationship between microbiome and salt intake. For each feature, a model will be fitted with the feature as outcome and salt intake (a binary variable with two categories: treatment and placebo) as covariate. The differential count (fold change difference) between treatment and placebo will be estimated for each feature (OTU). To adjust for the multiple testing of several OTUs, a false discovery rate penalty will be applied and only fold changes with an adjusted p-value (Benjamini-Hochberg multiple test correction) smaller or equal to 0.05 will be considered statistically significant.

The analysis describes above using a Poisson regression model assumes the features (OTUs) are independent but it has been shown that microbial communities do interact in such way that changes in one feature affect another feature. However, the number of interactions can be large due to the number of features, and not easily fitted in a conventional regression model. Therefore, a machine learning algorithm (Random Forest or Neural Network) will be used to investigate the combined response of the features to salt intake. These algorithms can incorporate multiple and complex interactions between features without making an assumption about their distribution. The features will be used as predictor variables to predict salt intake (a binary variable with two categories: treatment and placebo). The results will be presented as the area under the curve (AUC) of a receiver operating curve (ROC) that reflect how well the features can predict treatment and placebo. Because these ensemble techniques do not assume the predictors

variable (OTUs) are independent, no multiple testing penalty is required but rather cross-validation will be undertaken.

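### The crossover is sized on a paired t test, but several stated analyses drop or omit the pairing, and PWV has competing analyses with none named primary

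*Combined protocol and SAP*

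**What the plan says.** Section 4.2 justifies the crossover because each person provides her or his own comparison. Section 9.2 sizes it with a paired t test: PWV difference 0.6 m/s, SD 0.9 m/s, within-person correlation 0.3. The analyses are then described as follows.

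- **PWV, Section 9.2.** For normal data, "comparisons between the treatment (sodium intake) and control (placebo) groups will be made using paired" t-tests. It continues: "Tests for sodium intake effect on the primary outcomes without correction for period effect will be done using Mann-Whitney test on the differences". It then adds an evaluation of blood pressure, ambulatory pressure, biochemical markers, "vascular functions, and specific transcriptome and epigenome by using a linear mixed model, with subject as a random effect", with period, sequence and carryover accounted for.
- **PWV, Section 9.4.2.** "Its relationship with salt intake will be investigated through multiple linear regression with vascular function as outcome and salt intake" as a two-level exposure.
- **Blood pressure, Section 9.4.3.** The same kind of regression on treatment.
- **Non-normal data, Section 9.2.** When data are non-"normally distributed, the Mann-Whitney U test will be employed".
- **Microbiome, Section 9.4.2.** "For each feature, a model will be fitted with the feature as outcome and salt intake" as the covariate. Microbiome is not in the mixed-model list of Section 9.2.
- **Methylation, Section 9.4.3.** "The epigenetic effect of salt intake will be investigated through a two-sample t-test".

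Section 9 states that there will be no formal SAP. Section 9.4.1 promises in general terms to check assumptions and correct procedures.

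**The concern.** A crossover gains its efficiency only if the analysis uses the within-person contrast. The methylation test and the non-normal fallback are unpaired by name. The OTU models, which serve a primary endpoint, name no participant or period term.

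PWV, the other primary endpoint, has the opposite problem. Four descriptions exist, they give different p-values and intervals from the same data, and nothing says which one is the result. With no SAP to come, no later document is planned to settle it.

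The rank tests are also unclear. A test of salt-minus-placebo differences against zero is a one-sample test, so the Mann-Whitney label does not fit. A Mann-Whitney comparison of period differences between sequences does correct for period, yet the text says it does not. The period test is described in nearly the same terms: "Tests for period effect will be assessed using two-sample Wilcoxon tests on the differences between treatment groups". The text does not say which differences are meant in either case.

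**Working it through.** **Inputs (Section 9.2).** Difference 0.6 m/s, SD 0.9, correlation 0.3, two-sided 0.05, 80% power, 28 participants, 34 after 20% dropout, 40 planned. Section 12 reports 28 enrolled. Assumed: one end-of-period value per treatment, complete pairs, normal data, no period or carryover effect.

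**The plan's own figure.** SD of the within-person difference = 0.9 × √(2 × (1 − 0.3)) = 1.065. The normal approximation gives (1.960 + 0.842)² × 1.065² / 0.6² = 24.7. The noncentral t gives 27 (80.5% power), and 28 gives 82.0%. The stated 28 reproduces, and 28 × 1.2 = 33.6 gives the stated 34.

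**PWV regression with no participant term.** At 28:

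- Model SE = 0.9 × √(2/28) = 0.241
- True SE = 1.065 / √28 = 0.201
- Ratio = 1/√0.7 = 1.195, so the SE is about 20% too large
- True two-sided size ≈ 2 × (1 − Φ(1.96 × 1.195)) ≈ 1.9%; simulation gives 2.0 to 2.2%
- 95% CI half-width 0.48 m/s against 0.41 m/s paired

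Power (paired by noncentral t; unpaired from 100,000 simulated sets of correlated pairs per n):

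| Analysed | Paired | Unpaired |
|---|---|---|
| 22 | 71.2% | 59.4% |
| 28 | 82.0% | 72.0% |
| 34 | 89.0% | 81.2% |
| 40 | 93.5% | 87.9% |

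The row for 22 is 28 × 0.8 = 22.4, that is, the plan's dropout with nobody replaced; Section 7.2 says treated withdrawals are replaced. A mixed model with period, balanced sequences and complete data gives 81.9%, 89.0% and 93.5% at 28, 34 and 40, so adjusting for period costs almost nothing.

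**Mann-Whitney U fallback** (20,000 simulated trials of 28, no effects). It rejects 2.1% of the time on normal data, and 1.8% and 1.1% on lognormal data (log-SD 0.5 and 1.0, assumed). The signed-rank test rejects 4.7 to 4.9%, and a rank-sum on period differences 4.5%. Power on skewed data was not consistently worse for Mann-Whitney U than for signed-rank: 86.9% against 87.5% at log-SD 0.5, and 99.8% against 98.2% at 1.0. No power loss is claimed for the fallback.

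**Methylation at p < 9 × 10⁻⁸, n = 28.** The critical t is 7.23 paired (27 df) and 6.17 two-sample (54 df). The documents give no correlation for methylation, so this is a range by assumption. Difference detectable with 80% power, in SD units:

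| Correlation (assumed) | Two-sample | Paired |
|---|---|---|
| 0.3 | 1.87 | 1.86 |
| 0.6 | 1.85 | 1.41 |
| 0.9 | 1.83 | 0.70 |

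At 0.3 the smaller error is offset by the loss of degrees of freedom. At higher correlations it is not.

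**Which rank test to use.** Take no sodium effect, a 0.6 m/s period effect and an 18/10 split between sequences (assumed; Section 6.3 names no blocking). On normal data the false-positive rates are signed-rank 7.9%, paired t 8.1%, rank-sum on period differences 4.4%, and period-adjusted t 5.1%.

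**The case against.** The strongest reply is that Section 9.2 already gives PWV and blood pressure a random-subject mixed model, and that a multiple regression might include participant. That is fair. The PWV fault is the lack of a single named analysis, and the power figures hold only if the Section 9.4.2 regression has no participant term.

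Next, choosing among the PWV analyses does little damage. With balanced sequences and no period effect, taking the smallest p of the paired t, the treatment-only regression and the period-adjusted model gives a false-positive rate of 5.3% at 28 and 5.2% at 40. Adding three rank tests gives 6.3% and 6.6%. This stands under those assumptions, but the unadjusted tests do worse with a period effect and unequal sequences. Selection apart, the primary result is still not fixed in advance.

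Third, the error is conservative, planned enrolment still gives over 80% power, and the addendum does not say that 28 is final. All true. Skewed variables are also log-transformed first, so the fallback may seldom be needed.

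Finally, Section 9.4.1 promises to correct procedures. It does not say which analysis would then stand. None of this makes a two-sample t-test or an unpaired rank test suit a crossover, or supplies a participant term for the OTU models.

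**Conclusion.** The concern holds and should be fixed before analysis. The methylation test and the non-normal fallback discard the pairing, the OTU models as written do not use it, and PWV has no single primary analysis.

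For PWV, if the regression omits participant, about 10 percentage points of power are lost at 28 (82.0 − 72.0), which takes it below the 80% target. About 8 points are lost at 34 and 6 at 40, where it stays above 80%. These figures rest on the plan's SD and correlation. For methylation the cost runs from none at correlation 0.3 to large at 0.9, all assumed. No size is claimed for microbiome, RNA or the classifiers. The sample size calculation itself is sound.

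**What to change.** Before the treatment code is opened:

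- In Sections 9.4.2 and 9.4.3, name one primary analysis for PWV and blood pressure: a linear mixed model with treatment, period and sequence fixed and participant random. Say which visits enter it, and make Section 9.2 agree. A separate carryover term is not needed, because in two periods carryover cannot be told apart from sequence.
- For data still non-normal after log transformation, replace both Mann-Whitney descriptions of the treatment test with a rank-sum test on period-1-minus-period-2 differences, compared between sequences. Keep the signed-rank test on salt-minus-placebo differences only as an unadjusted sensitivity analysis.
- Add participant (random or blocking) and period to the OTU count models, and state both in the edgeR design.
- Replace the two-sample methylation test with a paired or participant-blocked one.
- For the classifiers, keep all of a participant's samples in the same cross-validation fold.

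The cost is analysis wording only. No new data or participants are needed.
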